#### **APPENDIX B: QUESTIONNAIRES**

#### THE KANSAS CITY CARDIOMYOPATHY QUESTIONNAIRE (KCCQ)

The following questions refer to your **heart failure** and how it may affect your life. Please read and complete the following questions. There are no right or wrong answers. Please mark the answer that best applies to you.

 Heart Failure affects different people in different ways. Some feel shortness of breath while others feel fatigue. Please indicate how much you are limited by heart failure (shortness of breath or fatigue) in your ability to do the following activities over the past 2 weeks.

	Place a	an X in one b	ox on each	n line			X
Activity	Extremely	Quite a bit	Modera	tely	Slightly	Not at all	Limited
for other reasons limite	d limite	d	limited	limited		limited	or did
not do the activity							
Dressing yourself	1	Ť	†	1	1		1
Showering/Bathing	Ţ	1	1	t	1	1	1
Walking 1 block on level ground	1	ſ	1	t	t	/	1
Doing yardwork, housework or carrying groceries	1	ţ	t	t	f		t
Climbing a flight of stairs without stopping	t	1 1		t		t	
Hurrying or jogging (as if to catch a bus)	7	j	1	1	1		1
	1			I	1		I

2. Compared with 2 weeks ago, have your symptoms of **heart failure** (shortness of breath, fatigue or ankle swelling)

changed? My symptoms of heart failure have become...

Much worse		Slightly worse	Not changed	Slightly better	Much better	I've had no symptoms
			-		over t	he last 2 weeks
†	t l	†	1	Ť	:	-

3. Over the past 2 weeks, how many times did you have **swelling** in your feet, ankles or legs when you woke up in

in the morning?

Every	3 or more times	1-2 times a	Less than once	Never over the
morning	a week, but not	week	a week	past 2 weeks
	everv dav			

f f f f

4. Over the past 2 weeks, how much has **swelling** in your feet, ankles or legs bothered you? In has been...

Extremely Quite a bitModeratelySlightlyNot at allI've had no swellingbothersomebothersomebothersomebothersome

5.	↑ Over the pa	† st 2 weeks , c	† on average, ho	† w many times	∱ has fatigue lin	† nited your abil	lity to do wł	nat you want?		
	of the time ce a Never o	Several tin ver	nes At le	east once a	3 or more tim	nes 1-2	times per	Less than		
the	e past 2	per day	ý	day	per week bu		veek	week		
we	weeks									
6.	
 
Over the past 2 weeks, how much has your fatigue bothered you? It has been
 
									
	Extremely ( bothersome b		Moderately bothersome	Slightly bothersome			had no fa t	tigue		
	Over the pas u wanted?	t 2 weeks , or	n average, hov	v many times ł	nas shortness	of breath lim	ited your al	oility to do what		
	of the time ce a Never o	Several tin ver	nes At le	east once a	3 or more tim	nes 1-2	times per	Less than		
the	e past 2	per day	ý	day	per week bu		veek	week		
we	eks				every da	ıy				
8.	8. Over the past 2 weeks, how much has your shortness of breath bothered you?									
	Extremely Quite a bitModeratelySlightlyNot at allI've had no shortnessbothersomebothersomebothersomebothersomeof breath									
	1	1	1	Ţ	1	1				
	9. Over the past 2 weeks , on average, how many times have you been forced to sleep sitting up in a chair or with at least 3 pillows to prop you up because of shortness of breath ?									
		3 or more time a week, k every day 1			than once a week	Never over past 2 we				
10. Heart Failure symptoms can worsen for a number of reasons. How sure are you that you know what to do, or whom to call, if your heart failure gets worse?										
	-	heart failure	gets worse?							

**sure** 1 1 1 1 11. How well do you understand what things you are able to do to keep your **heart failure** symptoms from getting worse? (for example, weighing yourself, eating a low salt diet, etc.)

Do not understand at all	Do not understand very well	Somewhat understand	Mostly understand	Completely understand
1	1 1	f	1	

12. Over the past 2 weeks, how much has your heart failure limited your enjoyment of life?

It has extreme				It has slightly It has not limited	l my
limited my	my enjoyment	moderately	limited my	enjoyment of life	
enjoyment of	of life quite	limited my	enjoyment of	at all	
life	a bit	enjoyr	nent of life	life	

13. If you had to spend the rest of your life with your **heart failure** the way it is right now, how would you feel about this?

Not at all	Mostly	Somewhat	Mostly satisfied	Completely
satisfied	dissatisfied	satisfied	sat	isfied
1	1	Ţ	1 1	

14. Over the past 2 weeks, how often have you felt discouraged or down in the dumps because of your **heart** failure?

I felt that way	I felt t	hat way	occasionally	I rarely felt that	I never felt that
all of the m	ost of the	felt that way	way	way	
time	time				

1 1 1

15. How much does your **heart failure** affect your lifestyle? Please indicate how your **heart failure** may have limited your

participation in the following activities over the past 2 weeks?

Please place an X in one box on each line

Activity not apply or did		Severely	Limited	Modera	tely	Slightly	Did not	Does
	limited	l c	quite a bit	limited	limite	ed	limit at all	not do for
other reasons								
Hobbies, recreation	onal							
activities	1	ſ	1	1		†	1	
Working or doing								
household chor	res	1	ſ	1	Ţ	ſ	f	
Visiting family or f	riends							
out of your hom	ne	1	1	1	1	ť	f	
Intimate relations	hips							
with loved ones	1	1	1	1	1		1	

Developed by John Spertus et al., Mid America Heart Institute, Saint Luke's Hospital, Kansas City, MO.

# NEW YORK HEART ASSOCIATION (NYHA)

Protocol Number	Site Number	Subject	Subject Initials	Visit Date
				(dd-MMM-yyyy) _

Examination	Not Done	Result		If abnormal findings, describe	
LXammation		Yes	No	n abhormar munigs, describe	
Class I: patients with no limitation of activities; they suffer no symptoms from ordinary activities					
Class II: patients with slight, mild limitation of activity; they are comfortable with rest or with mild exertion					
Class III: patients marked with limitation of activity; they are comfortable only at rest					
Class IV: patients who should be at complete rest, confined to bed or chair; any physical activity brings on discomfort and symptoms occur at rest					

## APPENDIX C: FINAL FORMULATION SKIN TEST

#### **Testing Materials:**

0.1 ml Aliquot of the Solution from Final Formulation Preparation (30 gauge needle syringe)

#### Procedure to be performed prior to infusion:

Testing is usually done on the volar surface of the forearm or lateral surface of the upper part of the arm.

1. Intradermal test: raise a bleb by intradermal injection using the 0.1 mL of aliquot. Read the test results at 10-15 minutes. A positive result disqualifies the subject.

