#### 8.1.1 Adverse Event (AE)

ICH E6 defines an AE as any untoward medical occurrence in a subject or clinical investigation subject administered a pharmaceutical product regardless of its causal relationship to the study stem cell administration. An AE can therefore be any unfavorable and unintended sign (including an abnormal laboratory finding), symptom, or disease temporally associated with the use of medicinal (investigational) product. The occurrence of an AE may come to the attention of study personnel during study visits and interviews of a study recipient presenting for medical care, or upon review by a study monitor.

All AEs including local and systemic reactions not meeting the criteria for "serious adverse events" will be captured on the appropriate CRF. Information to be collected includes event description, time of onset, clinician's assessment of severity, relationship to study product (assessed only by those with the training and authority to make a diagnosis) which would include MD, DO, PA or NP and time of resolution/stabilization of the event. All AEs occurring while on study must be documented appropriately regardless of relationship. All AEs will be followed to adequate resolution.

Any medical condition that is present at the time that the subject is screened will be considered as baseline and not reported as an AE. However, if it deteriorates at any time during the study, it should be recorded as an AE.

All AEs must be graded for severity and relationship to study product.

**Severity of Event:** All AEs will be assessed by the clinician using the following grading system of AE intensity.

- Mild: events require minimal or no treatment and do not interfere with the subject's daily activities.
- Moderate: events result in a low level of inconvenience or concern with the therapeutic measures. Moderate events may cause some interference with functioning.
- Severe: events interrupt a subject's usual daily activity and may require systemic drug therapy or other treatment. Severe events are usually incapacitating.
- Life threatening: any adverse drug experience that places the subject, in the view of the investigator, at immediate risk of death from the reaction as it occurred, i.e., it does not include a reaction that had it occurred in a more severe form, might have caused death.

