Changes in the severity of an AE will be documented to allow an assessment of the duration of the event at each level of intensity to be performed. Adverse events characterized as intermittent require documentation of onset and duration of each episode.

**Relationship to Study Products:** The clinician's assessment of an AE's relationship to investigational product is part of the documentation process, but it is not a factor in determining what is or is not reported in the study. If there is any doubt as to whether a clinical observation is an AE, the event will be reported. All AEs must have their relationship to investigational product assessed. In a clinical trial, the investigational product must always be suspect. To help assess, the following guidelines are used.

- Related There is a plausible temporal relationship between the onset of the AE and administration of the investigational product, and the AE cannot be readily explained by the subject's pre-existing clinical state, intercurrent illness, or concomitant therapies; and/or the AE follows a known pattern of response to the investigational product; and/or the AE abates or resolves upon discontinuation of the investigational product and, if applicable, reappears upon re-challenge.
- Not Related There is good evidence that the AE has an etiology other than the investigational product (e.g., pre-existing medical condition, underlying disease, intercurrent illness, or concomitant medication); and/or the AE has no plausible temporal relationship to administration of the investigational product (e.g., cancer diagnosed 2 days after treatment).

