## 8.2.1 Adverse Event Reporting Period

The study period during which all AEs and SAEs must be reported begins after initiation of study treatment and ends at study completion or study discontinuation/termination, whichever is earlier. Any condition present between consenting and time of treatment will be considered as baseline and not recorded as an AE. After this period, investigators should report only SAEs that are attributed to study treatment.

All AEs that are observed or reported prior to initiation of study treatment will be recorded as unrelated to treatment and those occurring after initiation of treatment will be recorded as treatment-emergent.

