## 8.2.2 Assessment of Adverse Events

Investigators will seek information on AEs and SAEs at each subject contact by specific questioning and, as appropriate, by examination. All AEs and SAEs, whether spontaneously reported by the subject or noted by authorized study personnel, will be recorded in the subject's medical record and on the appropriate AE or SAE CRF page.

Each recorded AE or SAE will be described by its duration (i.e., start and end dates), severity, regulatory seriousness criteria if applicable, suspected relationship to the investigational product, and actions taken.

Note: The investigator's assessment of causality for individual AE reports is part of the study documentation process. Regardless of the "Yes" or "No" causality assessment for individual AE reports, the sponsor will promptly evaluate all reported SAEs against cumulative product experience to identify and expeditiously communicate possible new safety findings to investigators and applicable regulatory authorities. Attribution of SAEs will be reviewed on an ongoing basis, and may be changed as additional clinical data emerge (e.g., reversibility of AE, new clinical findings in subject with AE, effects of retreatment, AEs in other subjects).

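### On its natural reading, Section 8.2.1 makes a reaction to the first (Day 7±3) skin test either not an adverse event or unrelated by rule, against Sections 8.1.1 and 8.2.2

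*Combined protocol and SAP*

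**What the plan says.** Randomisation is part of screening (Section 7.2.1). The assigned final formulation, cells or Lactated Ringer's Solution, is prepared after that (Synopsis, Administration of aMBMC). On the day of infusion a 0.1 mL aliquot of it is injected intradermally before the study product is administered (Sections 6.2 and 7.2.2). Appendix C defines a positive reading and states: "A positive result disqualifies the subject".

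Section 8.2.1 has three rules that bear on this moment:

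- On the reporting window: "The study period during which all AEs and SAEs must be reported begins after initiation of study treatment".
- On baseline: "Any condition present between consenting and time of treatment will be considered as baseline and not recorded as an AE".
- On causality: "All AEs that are observed or reported prior to initiation of study treatment will be recorded as unrelated to treatment".

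Other parts of Section 8 say something different. Section 8.1.1 sets baseline earlier: "Any medical condition that is present at the time that the subject is screened will be considered as baseline and not reported" as an adverse event. It also requires that "All AEs occurring while on study must be documented appropriately regardless of relationship", names local as well as systemic reactions, and asks for a relationship assessment of every event, on the footing that "In a clinical trial, the investigational product must always be suspect". Section 8.2.2 adds: "Investigators will seek information on AEs and SAEs at each subject contact by specific questioning and, as appropriate, by examination". It lists suspected relationship among the items to be described for each recorded event.

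**The concern.** The primary objective is the safety of an allogeneic cell product. For a subject randomised to cells first, the skin-test aliquot is the first contact with that product. If Section 8.2.1 is followed to the letter, a reaction at that moment is either left out of the adverse event record or entered with its causality already decided. Both outcomes remove the investigator's judgement that Section 8.1.1 asks for. Two sites following different sentences of 8.2.1 could record the same reaction differently.

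The label also has a downstream effect. The immediate telephone report in Section 8.3 depends on the investigator attributing a life-threatening or fatal event to the product, and a preset unrelated label works against that. Deaths are covered separately in Section 8.2.3.

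**Working it through.** The plan gives no figure on this point, so there is none to reproduce. The check is mainly a comparison of texts.

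**Step 1, order of events.** Consent and randomisation take place at Days 1 to 2. On Day 7±3 the skin test comes first and the infusion second. Sections 6.2 and 7.2.2 both put the test before administration. If study treatment means the infusion, the first skin test falls between consent and treatment.

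**Step 2, apply Section 8.2.1.** A reaction in that interval meets two rules at once. The baseline sentence says it is not an adverse event. The causality sentence says a pre-treatment adverse event is recorded, as unrelated. An event cannot be both unrecorded and recorded as unrelated. This contradiction lies inside 8.2.1 and does not depend on how study treatment is defined.

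**Step 3, compare with the other sections.**

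| Question | Section 8.2.1 | Elsewhere |
|---|---|---|
| When is baseline fixed? | Up to the time of treatment | At screening (8.1.1); at the start of the study (8.2.3, pre-existing conditions) |
| Is an event after screening and before infusion documented? | Not an adverse event, or recorded as unrelated | Documented, local reactions included (8.1.1) |
| Who decides relationship? | Fixed by rule as unrelated | Assessed for each event, product always under suspicion (8.1.1); suspected relationship described (8.2.2) |

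**Step 4, the Day 90 test.** Section 7.3 and Appendix A repeat the skin test at Day 90±7. By then treatment has been initiated, so the reporting window is open and a reaction is treatment-emergent. Cell aliquots are therefore handled differently by sequence:

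| Sequence | Aliquot at Day 7±3 | Aliquot at Day 90±7 | Handling of a reaction to the cell aliquot |
|---|---|---|---|
| Cells first | Cells | Lactated Ringer's Solution | Baseline, or unrelated by rule |
| Placebo first | Lactated Ringer's Solution | Cells | Reportable, treatment-emergent |

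The same first reaction to cells gets opposite treatment depending only on the randomised order.

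**Step 5, Appendix A.** The adverse event row is blank at Days 1 to 2 and first marked at Day 7±3. It does not separate the pre-infusion part of that visit from the rest, so it fits either reading.

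**Step 6, scale.** The inputs are 0.1 mL (Section 6.2 and Appendix C), 1 million cells/mL and 1.5 million cells/kg (Section 6.1), and 10 cell-first subjects (Synopsis, Sections 4.1 and 5.1).

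- Cells in the aliquot: 0.1 × 1,000,000 = 100,000.
- Share of the infused dose, for assumed weights of 60, 80 and 100 kg: 100,000 / 90 million = 0.11%; 100,000 / 120 million = 0.08%; 100,000 / 150 million = 0.07%.
- Chance of at least one reactor among 10 cell-first subjects, 1 − (1 − q)^10. The documents give no positive rate, so q is assumed:
  - q = 2%: 1 − 0.98^10 = 0.183
  - q = 5%: 1 − 0.95^10 = 0.401
  - q = 10%: 1 − 0.90^10 = 0.651

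**The case against.** The strongest reply is that study treatment is not defined. Section 8.1.1 frames an adverse event around administration or use of the product. If injecting the aliquot counts as starting treatment, the window in 8.2.1 is already open, the reaction is treatment-emergent, and the conflict over causality goes. This stands as a possible reading. The wording of Sections 6.2 and 7.2.2 points the other way, and nothing in the text settles it. The contradiction inside 8.2.1, and the different baselines in 8.1.1 and 8.2.1, remain on either reading.

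Three further replies carry some weight:

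- Section 8.2.1 does say pre-treatment events are recorded, so complete omission is not the only outcome. The unrelated label would still apply.
- A wheal with erythema is the test's own positive readout, so whether a local positive is itself an adverse event is a matter of judgement. But 8.1.1 names local reactions, and the rule in 8.2.1 would equally catch a systemic reaction to the aliquot.
- Section 9 promises a detailed analysis plan, and Section 5.3 puts the reason for early withdrawal on a case report form. A later plan can settle denominators and tables. It cannot recover causality judgements that were never collected.

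A reader might infer more than this, and the documents do not support it:

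- *Both skin tests are affected.* They are not; Day 90 falls inside the reporting window.
- *All 20 subjects are at risk of a lost or mislabelled reaction to cells.* Only the 10 cell-first subjects receive cells in the first test.
- *Appendix A contradicts 8.2.1.* It is ambiguous, no more.
- *A skin-tested, never-infused subject is certainly outside the safety analysis.* The Synopsis admits anyone given any part of a dose and does not say whether the aliquot counts.

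**Conclusion.** The point holds for the first (Day 7±3) skin test. Section 8.2.1 contradicts itself on pre-treatment events and differs from Section 8.1.1 on baseline. Its automatic unrelated label conflicts with the relationship assessment required by Sections 8.1.1 and 8.2.2. Followed literally, it would drop or mislabel a reaction to the first allogeneic exposure in up to 10 cell-first subjects, while the same reaction in placebo-first subjects would count as treatment-emergent.

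Two assumptions matter. The application to the skin test rests on study treatment meaning the infusion, which is the natural but unstated reading. The 18%, 40% and 65% chances of at least one reactor rest on assumed rates of 2%, 5% and 10%; they show only that the case is not remote at those rates, and say nothing about how often it will occur. No efficacy estimate or design figure changes. The defect is in the collection of primary safety data, so it should be corrected before data are gathered.

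**What to change.** - In Section 8.2.1, start adverse event and serious adverse event recording, with causality assessment, at the first skin test. Delete the automatic unrelated label for events after the aliquot. Use one definition of baseline, consistent with Section 8.1.1.
- In Section 7.2.2, add adverse event recording to the pre-infusion list. This also resolves the ambiguity in Appendix A.
- As a minor clarification, state in the Synopsis (Statistical Methods) whether the aliquot counts as part of a dose, and list skin-tested, never-infused subjects with the product tested.

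The disqualification rule in Appendix C is left as it is. The cost is a few sentences of wording, one listing and a few more recorded events.

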#### Interpretation:

A positive reaction includes a wheal of at least 4mm accompanied by erythema. Questionable results will be repeated.
